6.2 Venous Blood Draw

This is a routine procedure that is considered standard of care in clinical medicine. For participants who consent to provide a genetic sample in addition to the NMR, we will attempt to collect a single blood sample of approximately 15 ml (3 teaspoons) at the bedside or at an outpatient lab by clinical phlebotomy/study staff. This blood will be utilized for the enrollment consented NMR test and future genetic analysis. Blood for genetics will be discarded if a participant does not consent to genetics. The blood draw will be performed by trained personnel using universal precautions to protect both the participant and personnel. The risks to subjects are minimal, but may include pain, allergic reaction, infection, or bleeding at the needle stick site. These usually resolve without any specific medical therapy over the course of minutes to days.

6.3 Nicotine Metabolite Ratio (NMR) and Salivary Cotinine Testing

There are no known serious adverse effects from these tests. Nicotine metabolites (ratio of 3-hydroxycotinine to cotinine) will not be clinically reported beyond the study (i.e., NMR results only given to hospital team and provided to the PCP as described above).

7.0 Reporting of Adverse Events or Unanticipated Problems involving Risk to

Participants or Others

7.1 Specification of Adverse Events

An **Adverse Event (AE)** is defined as any untoward or unfavorable medical occurrence or undesirable experience associated with the use of a medical product in a human participant, including any abnormal sign (for example, abnormal physical exam or laboratory finding), symptom, or disease, temporally associated with participation in the research, whether or not it is considered related to participation in the research. AEs are graded as follows:

- Mild (no limitation of usual activities),
- Moderate (some limitation of usual activities), or
- Severe (inability to carry out usual activities)

AEs will be attributed according to the relationship to the study drug and/or procedure as:

- Unknown,
- Unrelated related,
- Possibly related,
- Related

An AE can therefore be any new sign, reaction, symptom, event, disease or a worsening in frequency or severity of a preexisting condition that occurs during the course of the study. Stable chronic conditions that were present prior to study entry and do not worsen are not considered AEs. An event is considered "related" if it is likely to have resulted from participation in the research study and is considered "unanticipated" when it was unforeseeable at the time of its occurrence. An **unanticipated problem (UP) involving risk to participants or others** is "Any event that was (1) unanticipated, (2) related, and (3) places participants or others at a greater risk of physical or psychological harm than was previously known or recognized."

A **serious adverse event** is defined as any adverse event that results in any of the following outcomes:

- Death
- life-threatening adverse event
- inpatient hospitalization or prolongation of existing hospitalization

- persistent or significant disability/incapacity
- congenital anomaly/birth defect.

Important medical events that may not result in death, be life-threatening, or require hospitalization may be considered a serious adverse event when, based upon appropriate medical judgment, they may jeopardize the patient or subject and may require medical or surgical intervention to prevent one of the outcomes listed in this definition. Examples of such medical events include allergic bronchospasm requiring intensive treatment in an emergency room or at home, blood dyscrasias or convulsions that do not result in inpatient hospitalization, or the development of drug dependency or drug abuse.

Unexpected adverse event is defined as any adverse event, the specificity or severity of which is not consistent with the risk information described in the general investigational plan.

Suspected Adverse Drug Reaction is any adverse event for which there is a reasonable possibility that the drug caused the adverse event. Reasonable possibility means there is evidence to suspect a causal relationship. It is considered unexpected if it is not consistent with the risk information described in the general investigational plan. A suspected adverse drug reaction will be defined as a recorded adverse event that is unexpected and deemed to be possibly, probably, or definitely related to the study drug.

7.2 Methods and Time for Assessing, Recording, and Analyzing Safety Parameters

Participant health status will be assessed during the baseline survey to document any chronic conditions or symptoms that existed prior to the study. This list will be reviewed and compared to reported events throughout the study. If the participant reports the same symptom, occurring at the same severity, during subsequent visits, the symptom should not be recorded as an Adverse Event (AE). However, if the event is new (not previously reported) or the severity has worsened, as determined by RA, then the AE should be reported.

In the case of unresolved AEs, study staff will update the AE log if they become aware of follow-up information.

All AEs will be assessed to determine if they meet criteria for a Serious Adverse Event (SAE). If the AE is serious, then appropriate reporting measures will be followed (see section 7.5). Investigators will consult with the IRB or NIH, if uncertain how to classify an event.

7.3 Procedures for Eliciting Reports of and for Recording and Reporting Adverse Events Medical conditions/pre-existing conditions (Table 3) and medical symptoms (Table 4) will be assessed at baseline. Medical symptoms will be assessed at follow up timepoints. All events, including changes in severity of any of the below mentioned medical symptoms, will be documented in a study database.

| | Medical Condition/Pre-existing Conditions Checklist |
|----|--|
| Α | Anemia or "low blood" |
| В | Congestive Heart Failure, also called weak heart or fluid on the lungs |
| С | Dementia or "Alzheimer's" |
| D | Diabetes or high blood sugar or "sugar" |
| Е | Liver Disease or a bad liver or Cirrhosis |
| F | Chronic Hepatitis B |
| G | Chronic Hepatitis C |
| Н | High cholesterol, lipids, or triglycerides |
| Ι | Hypertension or high blood pressure |
| J | Pancreatitis |
| К | Bad nerves in your feet causing pain and numbness (neuropathy) |
| L | Bad circulation in your legs or feet |
| М | Chronic lung disease (emphysema, asthma, chronic bronchitis or chronic |
| | obstructive lung disease) |
| N | Kidney Failure (or bad kidneys) |
| 0 | Stroke or "mini" stroke (Transient Ischemic Attack) |
| P | Pneumonia |
| Q | Shingles |
| R | TB or Tuberculosis |
| S | Post-Traumatic Stress Disorder |
| Т | Schizophrenia (hearing voices or seeing things that others |
| II | Depression (depressive disorder) |
| V | Anxiety (anxiety disorder) |
| W | Bipolar Disorder |
| | Any kind of Cancer (please list type below) |
| X | 1 2 3 4 5 |

Table 3: Medical Condition/Pre-existing Conditions Checklist

| v | Human Immunodeficiency Virus (HIV) or Acquired Immunodeficiency |
|---|---|
| r | Syndrome (AIDS) |

Table 4: Medical Symptoms

| Medical Symptoms | No | Yes→Date of the symptom(s)and severity of the symptom(s) (mild, moderate, severe) |
|--|----|--|
| A. Agitation and/or Irritability | | |
| B. Anger and/or hostility | | |
| C. Depressed mood | | |
| D. Anxiety (includes nervousness and panic attacks) | | |
| E. Restlessness | | |
| F. Insomnia | | |
| G. Abnormal dreams and/or nightmares | | |
| H. Headaches | | |
| I. Dizziness | | |
| J. Nausea and/or vomiting | | |
| K. Abdominal Pain | | |
| L. Fatigue | | |
| M. Hiccups | | |
| M. Cough | | |
| O. Mouth/Throat Irritation | | |
| P. Skin irritation | | |
| Q. Heartburn | | |

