4.0 Detailed Study Overview

Eligible participants are consented and enrolled into the study during their inpatient hospital stay, participants may also be enrolled in the ER and observation unit. Potential participants may also be recruited from procedural or other same day settings, such as same day surgeries, pre-op or admission planning visits, or health screenings involving imaging or procedures, such as lung cancer screening. This process includes: (1) Screening, enrollment, randomization; (2) Post-enrollment treatment support; (3) Outcome ascertainment via survey, biochemical samples, and passive follow up using health system databases.

1. Screening, enrollment, randomization

- Screening & enrollment
 - Initial Certified Tobacco Treatment Specialist (CTTS) (tobacco counselor) assessment and tobacco cessation counseling (with initial screening consent for NMR).
 - Confirmation of eligibility and assessment of inclusion and exclusion criteria by study RA, including NMR result and verification by pharmacy personnel through procedures such as insurance test claims.
 - The screening consent for the NMR test will occur before the main consent for study enrollment. To accommodate patients who are eligible for the study but who request more time to consider enrollment, study staff may obtain screening consent and then complete remaining enrollment steps such as blood draw at a later time (e.g., after study enrollment/clinic visit).
 - Patients will be randomized after study staff ensures they have met all criteria, including a valid NMR result. Blood for NMR testing may be collected via a fresh blood draw or using stored clinical samples. The NMR results will be analyzed after study staff completes the screening consent process with the patient. Study enrollment forms may be completed remotely, as needed, due to the time constraints of meeting participants in-person.
 - Study staff verifies patient contact information as part of the enrollment process. Due to time constraints, verification of contact information will be prioritized immediately after the screening consent process.

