 - If the main consent process takes place remotely, the consenting structure will remain the same (i.e. screening consent will be completed prior to the main consent). In this case, study staff will electronically provide a copy of all applicable study documents to the patient prior to verbally reviewing all elements of the consent. If no electronic delivery of the main consent is possible, a paper copy of the main consent will be provided in-person or mailed to the patient before verbal review over the phone.
 - Baseline survey may be completed remotely, as needed, due to the time constraints of meeting participants in-person.
 - Participants will be compensated with \$10 for the screening blood draw and \$40 for completion of the baseline survey.

- Randomization
 - Randomization will take place after a valid NMR has resulted. As noted above, in the case that a participant meets all other criteria, but NMR is not resulted, a patient may be consented but will not be randomized until after the NMR is resulted.
 - In the rare event that an NMR sample results as invalid (nicotine unable to be detected in sample) after the participant has been enrolled, the study team will obtain a backup sample within approximately a week of study enrollment. This sample will either be a stored clinical sample or the study team will coordinate a new blood draw. As needed, a courier service will be used to retrieve and deliver this sample.
 - Study medication will be provided by a VUMC or outside pharmacy after study enrollment either in-person or mailed to the participant's home. Participants who are unable to pay for their insurance co-pays for smoking cessation medication may be referred to existing programs at Vanderbilt University Medical Center to facilitate obtaining medication. In the infrequent instance where charges related to the study are mistakenly billed to the participant, the study team will reimburse the participant via a gift card.
 - Participant will be provided with study information including a copy of the consent document and, for those randomized to the MIST arm, information on the NMR test.

2. Post-enrollment treatment support

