6.1 Smoking Cessation Medication Side Effects

In order to protect against potential risks associated with smoking cessation pharmacotherapy, this study involves FDA-approved medications according to label usage for smoking cessation aids. There is a risk of adverse side effects from FDAapproved smoking cessation medications, but this risk is not higher than that experienced by people taking the same medications outside of this research study.

The smoking cessation treatments in this study consist of counseling from trained tobacco treatment counselors in combination with safe and effective FDA-approved medications prescribed by the participants' inpatient team and/or PCPs. This combination of medication and counseling is the standard of care for smoking cessation treatment, and for those who successfully quit smoking, results in prolongation of life and improved quality of life.

Medication eligibility will be reviewed by two separate members of the study team (e.g., CTTS and PI or study coordinator and PI) to identify potential contraindications to nicotine replacement or varenicline.

- Nicotine replacement therapy (NRT): NRT is generally very safe, and several preparations have been sold over the counter for decades which is an indication of the FDA's view of their relative safety. The most common side effect of the patch is skin irritation or itching where the patch is applied, which is commonly managed by rotating patch sites and/or applying an OTC corticosteroid cream (such as 1% hydrocortisone). For nicotine lozenge/gum the most common side effects are mouth irritation, heartburn, hiccups. Many of the side effects of the lozenge/gum can be avoided by proper technique of the medication. For the nicotine inhaler and nasal spray, the most common side effects can include mouth/throat irritation, coughing, runny nose, watery eyes. In rare cases dizziness, headache, nausea, and rapid heartbeat can occur.
- Varenicline: Common side effects of varenicline include nausea and other gastrointestinal symptoms, sleep disturbance, and vivid dreams. The FDA-mandated EAGLES trial has established these medications as safe and effective. [52]

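### Section 7.2's rule for recording adverse events is narrower than the definition in 7.1, so some events that meet 7.1 would not be classed as AEs

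*Combined protocol and SAP*

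**What the plan says.** Section 7.1 defines an AE as any new sign, symptom or event, or "a worsening in frequency or severity of a preexisting condition that occurs during the course of the study". Its only exemption is: "Stable chronic conditions that were present prior to study entry and do not worsen are not considered AEs".

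Section 7.2 gives the working rule. The baseline survey is to "document any chronic conditions or symptoms that existed prior to the study", and later reports are compared with that list. The rule then says: "If the participant reports the same symptom, occurring at the same severity, during subsequent visits, the symptom should not be recorded" as an AE. An event is reported "if the event is new (not previously reported) or the severity has worsened, as determined by RA".

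Section 7.3 has the Table 4 symptoms asked at baseline and at the follow-up time points, with a date and a severity grade, and has events documented in a study database. Table 4 has no field for frequency.

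On setting, Section 4.0 says "Eligible participants are consented and enrolled into the study during their inpatient hospital stay". It also allows emergency, observation and same-day settings, and adds: "Baseline survey may be completed remotely, as needed, due to the time constraints of meeting participants in-person". On drug effects, Section 6.1 says "Common side effects of varenicline include nausea and other gastrointestinal symptoms, sleep disturbance, and vivid dreams", and lists skin, mouth and throat irritation, hiccups and heartburn among the effects of nicotine replacement.

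**The concern.** Staff will apply 7.2, because it is the instruction on what to write down. If it is narrower than 7.1, events that the protocol itself defines as AEs will not enter the AE record.

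The setting makes this more than a drafting matter. Patients in hospital may have nausea, poor sleep, anxiety or cough from their illness or from nicotine withdrawal. Several Table 4 items are also the known effects of the two treatments. A transient symptom on the ward can therefore stop the same symptom from counting later, when it appears on medication.

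Other steps depend on the AE record. The DSMB monitors adverse events (7.5). A suspected adverse drug reaction is defined as a subset of recorded AEs (end of 7.1). The check for seriousness in 7.2 starts from AEs. Side effects are also part of the trial's rationale: Section 2.1 cites more side effects without cessation benefit for varenicline in slow metabolizers, and Section 2.3 stresses how far the drugs' side-effect profiles differ.

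**Working it through.** The plan states no figure to reproduce. The check sets the two rules side by side, using 7.1, 7.2 and the Table 4 fields.

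| Situation at follow-up | Under 7.1 | Under 7.2 | Agree? |
|---|---|---|---|
| Chronic condition, unchanged | Not an AE | Not recorded | Yes |
| Baseline symptom, worse severity | AE | Recorded | Yes |
| Baseline symptom, same severity, more frequent | AE | Not recorded | No |
| Acute baseline symptom, resolved, returns at the same severity | Can be a new symptom; not a stable chronic condition | Not recorded: same symptom, same severity, already reported | No |
| As above, but returns milder | Can be a new symptom | Not expressly barred, but neither new in 7.2's sense nor worse | Unclear |

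Two further points follow from the forms.

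- Table 4 asks for date and severity only, so the frequency part of 7.1 has no item behind it in the checklist.
- There are three severity grades. A symptom graded severe at baseline cannot be graded worse, so under 7.2 its return could not qualify on severity.

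**Size.** The documents give no baseline symptom prevalence, severity mix or expected AE rate, so the following only shows the mechanism. Let R be the true rate, in an arm, of events that meet 7.1, and let b be the share of those events that 7.2 bars, taken as equal in both arms.

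- Recorded rate = R × (1 − b)
- Recorded difference = (R₁ − R₀) × (1 − b)
- Recorded ratio = R₁(1 − b) / R₀(1 − b) = R₁ / R₀

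With assumed true rates of 20% and 10% (difference 10 points, ratio 2):

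| Assumed b | Recorded rates | Difference | Ratio |
|---|---|---|---|
| 10% | 18% vs 9% | 9 points | 2 |
| 30% | 14% vs 7% | 7 points | 2 |
| 50% | 10% vs 5% | 5 points | 2 |

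Counts and absolute differences fall in proportion to b, and the ratio is unchanged. If b differed between arms the ratio would move too, but nothing in the documents indicates a direction.

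**The case against.** The case for leaving 7.2 alone has several parts.

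- **New or worse than baseline is a common convention.** This stands as a general remark. The difficulty is that 7.2 is narrower than this protocol's own definition.
- **The word chronic in 7.2's baseline list might govern symptoms as well as conditions**, which would match the exemption in 7.1. This reading is weak, because 7.3 collects every Table 4 symptom at baseline without limiting it to chronic ones.
- **7.2 does not mention resolved and recurrent symptoms, and leaves the decision to the research assistant.** True, but its test for a new event is that it was not reported before, and a recurrent symptom fails that test as written.
- **The data are not lost.** This stands. Symptoms are collected with date and severity, and 7.5 lets the DSMB review safety data without confining it to filtered AE counts. However, no section commits to tabulating the unfiltered symptoms, and Section 9 plans no safety analysis.
- **Not every baseline is taken in an acutely ill inpatient, and the recall period of the baseline items is not shown.** Both stand.
- **The practical consequence is limited.** Many affected events would be mild, known effects of approved drugs, and expedited IRB reporting in 7.4 concerns serious, unexpected, possibly related events. This stands and limits the importance of the point.

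A reader might go further and infer that the plan hides drug side effects, or that it erases a specific large part of the difference between arms. The documents support neither. The symptoms remain in the database. Any percentage would need invented inputs, and would overstate the loss if it assumed that every baseline symptom had resolved, since a persisting stable chronic symptom is not an AE under 7.1 either. A contrast between drugs is also not a contrast between arms: both arms use both drugs, and the pilot in Section 3.0 had about 60% varenicline prescription in each.

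**Conclusion.** The point holds as an inconsistency with a practical effect. Section 7.2 drops worsening in frequency, and it widens the exemption from stable chronic conditions to any symptom reported at baseline at the same severity, including one that resolved and came back. Followed as written, it leaves some events that meet 7.1 out of the AE record, and AE counts are biased downward.

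The size is unknown. It depends on how many participants report a Table 4 symptom at baseline, how often that symptom resolves, and how often it returns at the same grade. None of these is given. That relative comparisons survive rests on the assumption that the loss is equal in the two arms. The primary abstinence analysis is not affected. The point merits correction because the remedy is cheap and the AE record feeds safety oversight.

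**What to change.** Reconcile 7.2 with 7.1 as follows.

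1. Limit the exemption to preexisting conditions or symptoms that are stable and persisting.
2. Count a symptom that resolved and recurred after enrollment as new, identified from the Table 4 date field. The form should make clear that this date is the date of onset, since Table 4 does not say.
3. Count worsening in frequency, as 7.1 does. This needs a short frequency item in Table 4 at baseline and at each follow-up.
4. Report Table 4 symptom frequencies by arm and time point, unfiltered by baseline status, to the DSMB and in the final report, beside the AE counts.

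The cost is revised wording, one added survey item and more mild AEs to log. Item 4 uses data already planned for collection, and would still show participants' symptoms by arm if the AE rule were left as it is. Changing the recall period of the baseline symptom questions is optional, because the documents do not show their current wording.

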7.4 Adverse Event (AE) Reporting

All adverse events (AE) and unanticipated problems (UP) will be reported to the IRB by the study team within the mandated time frames. Ultimately, the PI and study coordinator will review any serious adverse events and report them to the IRB and NIH.

The PI will report AE and UP to the VUMC IRB in accordance with IRB policies:

- Required reporting to the IRB within 7 calendar days of the Investigator's knowledge of the problem which includes serious adverse events, injuries, side effects, deaths, or other problems occurring at VU, VUMC or other locations in which the Investigator is responsible for the conduct of the research and the VUMC IRB serves as the IRB of Record:
 - Any serious AE that in the Investigator's opinion was unanticipated or unexpected, involved risk to participants or

others and was at least possibly related to the research procedures; and/or

- Any noncompliance with the IRB-approved protocol that increased risk or affected the participant's rights, safety, or welfare.
- Any UP listed above requires reporting to the IRB even after the participant has completed the study or after the participant has withdrawn from the study including after study closure.

